6.2.2 Exclusion Criteria

No exclusion criteria will be applied.

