6.3.2 Characterization Variables

Characteristics of new inebilizumab users at index date will include demographics, comorbidities, NMOSD-related clinical characteristics (disease duration, NMOSD core

¹The use of Orphanet coding system for rare diseases (<https://www.orpha.net/>) will be explored in the SAP as appropriate

syndromes, differential diagnoses, NMOSD-associated conditions, history of relapses), previous immunosuppressive therapies, and inebilizumab initiation characteristics (setting of healthcare and specialty of prescribers and treatment indication). Please note that the list of characterization variables may be refined based on the databases availability and specificity. Detailed operational definitions and lists of local codes will be provided in the SAP.

Demographic characteristics include sex, age at the index date and race/ethnicity, depending on availability.

Comorbidities will be assessed by the presence of an ICD-9/ICD-10 codes during the baseline period in the data sources (Table 6 in Annex 3). The codes for the following specific conditions are provided (Table 6 in Annex 3):

- Coronary heart disease
- Heart failure
- Cerebrovascular disease
- Lung disease
- Renal disease
- Rheumatic disease
- Diabetes
- Hypertension
- Malignancy
- Osteoporosis
- Anxiety
- Depression
- Skin ulcers/cellulitis
- Renal transplantation
- Infections

Charlson comorbidity index (CCI) (11) will be retrieved as an overall measure of the burden of concomitant diseases. A CCI code list will be provided in the SAP.

Prescriber of inebilizumab will be described in terms of the type of facility he/she works at (hospital or other) and specialty (e.g., Neurology, Neuroradiology, Ophthalmology, Rheumatology, Psychiatry, or other), if available.

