6.4.4 Italy

The Italian Multiple Sclerosis & Related Disorders Register (*Registro Italiano Sclerosi Multipla e Patologie Correlate* [RISM]) was officially established in 2015. As of February 2023, the register was actively covering 133 MS centers, corresponding to a total of 80,353 patients, of which 273 are diagnosed with NMOSD. Since July 2022, the

register comprises a module for the collection of information on NMOSD, and has projects dedicated to NMOSD patients (22). Nonetheless, data on NMOSD patients were collected previous to 2022, without a specific module implemented. The data are collected from participating centers through a web-based system developed for the study, available at the IMS&RD website. Data are collected from accrual to exit of database, which may occur at date of death, when patient moves to a center outside of the covered network or withdraws their consent to participate. The data are centrally monitored to ensure quality of data, completeness, accuracy, and consistence (23). Requests to access the data are evaluated by the Scientific Committee, composed by clinicians, methodologists, representatives of MS centers, and of the Italian Neurological Society (23).

To ensure the collection of sufficient data for the clinical characterization of the single patient mandatory variables collected by the register include patient identification, demographics, vital status, disease onset date, diagnosis date, relapses, treatments and severe adverse events. This minimum dataset may be completed with an extension to optional information on family history, comorbidities, laboratory tests and MRI. Furthermore, the register has data on patient's unique personal identifier, to avoid inclusion of the same patient by more than 1 center. Diagnosis information is available and captured with ICD-9-CM coding system.

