6.7.2.3 Objective 3: Incidence of AESI

The AESI evaluated in this study include the following categories: serious infections, opportunistic infections, hepatitis B reactivations, infusion related reactions, and malignancies. Analysis of AESI will include estimation of the cumulative incidence (i.e., risk), incidence rate, and time to AESI onset ([Table 5](#)). All analysis for AESI events (i.e., cumulative incidence, incidence rate and time-to-onset) will be performed using an intention-to-treat approach i.e., patients will be considered exposed regardless of subsequent discontinuation.

The cumulative incidence (with 95% CI) will be calculated separately for each AESI category considering the overall study population. For all AESI categories, except infusion related reactions, the cumulative incidence (with 95% CI) will be calculated as the total number of incident reports of AESI during the follow-up divided by the total number of patients. An algorithm to identify incident reports of AESI will be developed and described in the SAP. For infusion related reactions, the cumulative incidence (with 95% CI) will be calculated as the total number of all reports of infusion related reactions on the day of infusion (if date of inebilizumab administration is available) or during the first 3 days following prescription/dispensation (if date of inebilizumab administration is not available), divided by the total number of patients in the overall study cohort. Additional details of this calculation will be provided in the SAP.

The cumulative incidence estimates for each AESI category, except infusion related reactions, may also be calculated for shorter periods e.g., in monthly intervals after index date. In this case, the cumulative incidence in the first month after index date would consider patients with AESI reports in the first month in the numerator and patients with complete 12-month follow-up in the denominator. The cumulative incidence in the second month would consider patients with reports recorded only in the second month in the numerator and patients with complete 12-month follow-up included in the denominator. Due to the limited sample size, the time intervals may need to be clustered into e.g., 3-month intervals with the numerator and denominator adjusted accordingly. If sample size permits, the difference (with 95% CI) in cumulative incidence between 2 time periods of observation may be calculated.

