The incidence rate and time to onset of AESI will be estimated in the overall study population. The incidence rates will be estimated separately for each AESI category, except infusion related reactions, as the total number of first reports of an AESI divided by the time at risk of the patients. The patients' time at risk will be counted from the initiation of inebilizumab treatment until occurrence of AESI, end of the 12-month follow-up or censoring. Incidence rate will be expressed as the number of first reports of an AESI per 1,000 patient-months.

Kaplan-Meier estimates of the median time from index date to AESI onset will be provided separately for each AESI category, except infusion related reactions, if number of events allows. If there is no AESI during the follow-up, the patient will be censored at the end of follow-up. Descriptive statistics on the time-to-event will be provided in further detail in the SAP.

Table 5 Overview of estimates of incidence and time to event defined for objective 3.

AESI category	Estimate	Time at risk	Event	Population
Infusion related reactions	Cumulative incidence	Day of infusion if date of inebilizumab administration available or 3 days following prescription/dispensation	All recorded reactions	Overall population
Serious Infections / Opportunistic infections	Cumulative incidence	12 months	All recorded infections during the follow-up	Overall population
	Cumulative incidence	Short periods	First infection during follow-up	Patients with complete 12-month follow-up
	Incidence rate	From index date to AESI, end of follow-up or censored*	First infection	Overall population
	Time to event	From index date to AESI end of follow-up or censor*	First infection	Overall population
Hepatitis B reactivations	Cumulative incidence	12 months	All recorded reactivations during the follow-up	Overall population
	Cumulative incidence	Short periods	First reactivation	Patients with complete 12-month follow-up
	Incidence rate	From index date to AESI end of follow-up or censor*	First reactivation	Overall population
	Time to event	From index date to AESI, end of follow-up or censor*	First reactivation	Overall population

AESI category	Estimate	Time at risk	Event	Population
Malignancies	Cumulative incidence	12 months	All recorded malignancies during the follow-up	Overall population
	Cumulative incidence	Short periods	First malignancy	Patients with complete 12-month follow-up

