ANNEX 3. ADDITIONAL INFORMATION

Table 6 List of Comorbidities

Comorbidities	Diagnosis ICD-9-CM Codes*	Diagnosis ICD-10-CM Codes*
Coronary heart disease	410.xx, 411.xx, 412, 413.x, 414.xx	I21.xx, I24.x, I25.2, I20.x, I25.xxx
Heart failure	398.91, 402.01, 402.11, 402.91, 404.01, 404.03, 404.11, 404.13, 404.91, 404.93, 428.xx	I09.81, I11.0, I13.0, I13.2, I50.xx
Cerebrovascular disease	430, 431, 432.x, 433.xx, 434.xx, 435.x, 436, 437.0, 437.1, 437.8, 437.9, 438.xx, 997.02	I60.9, I61.9, I62.xx, I63.xx, I65.xx, I66.xx, G45 [excl. G45.4], I67.84, I67.2, I67.81, I67.82, I67.89, I67.9, I69.8, I69.9x, I97.81, I97.82
Lung disease	493.00-493.02, 493.10-493.12, 493.20-493.22, 493.81, 493.82, 493.90-493.92, 491.0, 491.1, 491.20-491.22, 491.8, 491.9, 492.0, 492.8, 496, 490, 494.0, 494.1, 495.0-495.9, 500, 501, 502, 503, 504, 505, 506.4	J45.2x-J45.5x, J45.9xx, J41.x, J42, J43.x, J44.x, J60, J61, J62.x, J63.x, J64, J65, J66.x, J67.x, J68.4
Renal disease	403.01, 403.11, 403.91, 404.02, 404.03, 404.12, 404.13, 404.92, 404.93, 582.x, 583.0-583.7, 585.x, 586, 588.xx, V42.0, V45.1x, V56.x	I12.0, I13.11, I13.2, N03.x, N05.9, N05.2, N05.5, N17.1, N18.x, N19, N25.xx, Z94.0, Z99.2, Z91.15, Z49.xx
Rheumatic disease	446.5, 710.0-710.4, 714.0-714.2, 714.81, 725	M31.5, M31.6, M32.xx, M34.xx, M35.0x, M33.xx, M05.xxx, M35.3
Diabetes	249.xx, 250.xx, 357.2, 362.0x, 366.41, 648.0, E932.3, V58.67	E08.xx, E09.xx, E10.x, E11.xx, E13.xx, O24 [excl. O24.4], Z79.4
Hypertension	401.x, 402.xx, 403.xx, 404.xx, 405.xx	I10, I11.x, I12.x, I13.xx, I15.x, I16.x
Malignancy	140.x-171.x, 174.x-195.x, 200.x- 207.x, 209.0x - 209.3x, 173.00, 173.09, 173.10, 173.19, 173.20, 173.29, 173.30, 173.39, 173.40, 173.49, 173.50, 173.59, 173.60, 173.69, 173.70, 173.79, 173.80, 173.89, 173.90, 173.99, 796.76, 795.06, 795.16	C00.x-C43.x, C4A.x, C45.x- C96.x, C44.00, C44.09, C44.10x, C44.19x, C44.20x, C44.29x, C44.30x, C44.39x, C44.40, C44.49, C44.50x, C44.59x, C44.60x, C44.69x, C44.70x, C44.79x, C44.80x, C44.89, C44.90, C44.99, R85.614, R87.614, R87.624
Osteoporosis	733.0x, 733.1x	M80.xxxx, M81.x
Anxiety	300.2x, 300.0x, 300.3	F40.xxx, F41.x, F42.x
Depression	296.21, 296.22, 296.23, 296.26, 296.31, 296.32, 296.33, 296.36	F32.x, F33.xx
Skin ulcers/cellulitis	681.00, 681.10, 681.9, 682.x, 707.xx	L03.01x, L03.03x, L03.11x, L03.21x, L03.31x, L03.81x, L03.90, L89.x, L97.x

Comorbidities	Diagnosis ICD-9-CM Codes*	Diagnosis ICD-10-CM Codes*
Renal transplantation	55.69, V42.0	Z94.0

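### The Table 6 code row for baseline malignancy is narrower in ICD-9-CM than in ICD-10-CM, and neither column matches the malignancy AESI in Table 12

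*Protocol*

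**What the plan says.** **Baseline.** Protocol section 6.3.2 says: "Comorbidities will be assessed by the presence of an ICD-9/ICD-10 codes during the baseline period in the data sources". It points to Table 6 in Annex 3, and section 6.7.2.1 reports the result under Objective 1. The Malignancy row of Table 6 begins "140.x-171.x, 174.x-195.x, 200.x- 207.x, 209.0x - 209.3x, 173.00, 173.09" in ICD-9-CM and "C00.x-C43.x, C4A.x, C45.x- C96.x, C44.00, C44.09, C44.10x, C44.19x" in ICD-10-CM. Each column then lists further skin codes and three codes from other chapters.

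**Outcome.** Table 12 in Annex 3 defines the malignancy AESI by two unbroken ranges, 140-209 and C00-C96. For the 12-month cumulative incidence, Table 5 takes as the event "All recorded malignancies during the follow-up". Section 6.7.2.3 speaks of incident reports and adds: "An algorithm to identify incident reports of AESI will be developed and described in the SAP". Section 6.2.2 states: "No exclusion criteria will be applied".

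**Coding system.** Section 6.4.4 says of the Italian register: "Diagnosis information is available and captured with ICD-9-CM coding system". Footnotes to Tables 6 and 12 say that the printed codes will be translated to local versions in the SAP.

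**The concern.** One row of Table 6 is meant to measure one condition in every source, but the ICD-9-CM column drops whole categories that the ICD-10-CM column does not drop. The same history can then be present or absent at baseline depending on the coding system. That makes the Objective 1 malignancy figure too low in the ICD-9-CM source and not comparable across countries.

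The row is also narrower than the outcome. Patients with prior cancer are not excluded. The limitations section says that NMOSD is associated with cancer and that a year may be too short to detect some malignancies. A reader of the malignancy AESI will therefore want to know who already had cancer. A baseline variable that cannot see some of the codes the outcome counts does not answer that.

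**Working it through.** The check is a set difference on the printed codes. The point rests on no sample-size or power figure.

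**1. ICD-9-CM, Table 12 minus Table 6**
- Table 12: 140 to 209, which is 70 three-digit categories.
- Table 6 as full ranges: 140-171 (32), 174-195 (22) and 200-207 (8), together 62.
- Table 6 in part: 173 (20 listed codes, fifth digit only 0 or 9) and 209 (only 209.0x to 209.3x), which is 2 categories.
- Wholly absent: 70 - 62 - 2 = 6 categories, namely 172, 196, 197, 198, 199 and 208.
- Partly absent: 173.xx codes not ending in 0 or 9, and 209.4 upward.

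**2. ICD-10-CM, Table 12 minus Table 6**
- Table 12: C00 to C96, which is 97 categories.
- Table 6 as full ranges: C00-C43 (44) and C45-C96 (52), together 96.
- The one remaining category, C44, enters through 20 listed subcodes with the same 0/9 pattern. Only the unlisted C44 subcodes are absent.

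**3. Table 6, column against column**
Table 12 pairs 140-209 with C00-C96 as the same outcome. On that pairing, the Table 6 ICD-10-CM column covers every category at least in part, and the ICD-9-CM column omits six outright. The skin pattern is common to both columns. The other gaps have no parallel in the ICD-10-CM ranges.

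**4. Table 6 minus Table 12**
Six baseline codes lie outside the outcome ranges: 796.76, 795.06, 795.16, R85.614, R87.614 and R87.624.

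**5. Reach**
The protocol states ICD-9-CM use for Italy. In Table 4, Italy has 39,908,080 of 110,687,896 covered adults: 39,908,080 / 110,687,896 = 0.361, or 36%. This is a share of population, not of expected inebilizumab users.

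**6. One patient followed through the definitions**
Take a patient in an ICD-9-CM source coded 172.x before and after index. At baseline, Table 6 gives no malignancy. In follow-up the code meets the Table 12 definition. Whether it becomes an incident event depends on the algorithm:
- look-back with Table 12 codes: the earlier 172.x is found, so the case can be recognised as prevalent;
- look-back with Table 6 codes: the earlier 172.x is not found, so the case is taken as new;
- no look-back: the case is counted, but so is a prior cancer that Table 6 does list, such as 174.x.

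The mismatch produces a false event only in the second case.

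**7. Scale, as an illustration**
Section 6.5 uses 400 patients and 1% incidence. Its Table 3 entry reproduces: 1.96² × 0.01 × 0.99 / 0.01² = 380.3, printed as 380. At 400 patients, 1% is 4 events. One prevalent cancer wrongly counted adds 1/400 = 0.25 percentage points (4 to 5 events, +25%). The 95% half-width at that size is 1.96 × √(0.01 × 0.99 / 400) = 0.98 percentage points.

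**The case against.** The strongest reply is that Table 6 is a descriptive comorbidity list and need not equal an outcome definition. The 0/9 skin pattern is itemised in the same way in both columns and looks deliberate. Local translation is still to come, and no source is said to use ICD-10-CM: the protocol names the German modification for Germany, WHO ICD for Dutch hospitals and ICD-10 for French hospital data. Whether the C44 gap survives translation is therefore unknown. In Italy, comorbidities are optional items in the register, so baseline malignancy may be incomplete there whatever the code list.

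Much of this stands. It limits the ICD-10 side of the point to some C44 subcodes, and it means that the skin subset may be a choice rather than a slip. It does not explain 172, 196 to 199 and 208, which are missing from one column only. Translating a list with gaps keeps the gaps, and optional recording is no reason to drop codes that were recorded.

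A reader might go further and infer that a cancer unseen at baseline will be counted as an event on treatment. The protocol does not support that. Nothing in it makes Table 6 the look-back list, and the algorithm is expressly left to the SAP. Nor would the mismatch be the sole cause, since a prior cancer that Table 6 does list would also be counted unless the algorithm removed it. It would equally be wrong to say that skin cancers are invisible in every source: C43, C4A and 20 C44 entries are in the ICD-10-CM column, and twenty 173.xx codes are in the ICD-9-CM column.

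**Conclusion.** The point holds as a code-list inconsistency with a definite but limited effect. On the printed definitions, the Malignancy row of Table 6 is narrower in ICD-9-CM than in ICD-10-CM by six whole categories and by 209.4 upward. Both columns are narrower than Table 12 in the skin codes. The Objective 1 malignancy result would be under-recorded in the Italian source relative to the ICD-10 sources, and baseline history would not line up with the AESI.

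This assumes that the lists are carried into local codes as printed and that the Italian register holds at least some of the omitted codes. The effect on the incidence of malignancy is conditional: false events may arise if the SAP looks back with Table 6. No count of them can be given, because the protocol states neither how many patients have such a history nor how often it is recorded again within 12 months. The 0.25 points per case is a unit of scale. The 1% behind it is a generic planning value, not a malignancy rate.

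**What to change.** - In Table 6, add 172, 196 to 199 and 208 to the ICD-9-CM malignancy codes so that the two columns cover the same ground.
- Decide on 209.4 upward and on the subset of 173 and C44 codes once, and apply the decision in both Table 6 and Table 12. If a narrower skin list is intended at baseline, say so and give the reason.
- Say whether the six Table 6 codes outside the Table 12 ranges are meant to count as malignancy.
- State in section 6.7.2.3 that the incident-malignancy algorithm looks back with the Table 12 AESI codes, and leave its details to the SAP.

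The cost is an edit to code lists in Annex 3 and the SAP before analysis, plus one added sentence. The downside is that baseline malignancy prevalence rises slightly.

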4 RATIONALE AND BACKGROUND

4.1 Background

Neuromyelitis optica spectrum disorder (NMOSD; also known as Devic's syndrome and previously known as neuromyelitis optica [NMO]) is a rare, chronic, autoimmune, inflammatory disorder of the central nervous system, characterized by attacks of optic neuritis and longitudinally extensive transverse myelitis and, less frequently, affecting the brain and brainstem (1). Commonly reported symptoms include ocular pain, unilateral or bilateral loss of visual acuity that can lead to blindness, loss of sensation, weakness (including paraplegia), bladder and bowel dysfunction, paroxysmal tonic spasms of the trunk and limbs, and Lhermitte's phenomenon (1). Up to 90% of patients with NMOSD have recurring episodes of optic neuritis and/or myelitis rather than following a monophasic course (2). Attacks can be severe and result in blindness, paralysis, and even death due to neurogenic respiratory failure (3). An important paraclinical feature of NMOSD seen in 80% patients and used to help differentiate the condition from multiple sclerosis (MS) is the presence of serum autoantibodies against aquaporin-4 (AQP4) (i.e., AQP4-immunoglobulin [Ig]G or NMO-IgG) (4).

Worldwide, incidence rates of adult NMOSD are reportedly between 0.04-0.73/100,000 person-years (5), while the prevalence of NMOSD in adults is approximately 0.5-4/100,000 and may be up to 10/100,000 in certain racial groups (6). NMOSD can occur at any age, and disproportionately affects females (70%-90%), with a mean age of onset of approximately 40 years (6).

Treatment of NMOSD comprises 2 main goals: recovery from acute attacks and prevention of future attacks (relapse) as well as prevention of sequelae.

Recently, inebilizumab, an anti-CD19 B-cell depleting antibody, was approved for the treatment of NMOSD in AQP4-IgG seropositive patients in the US, Japan, and South Korea, and in November 2021 the Committee for Medicinal Products for Human Use of the European Medicines Agency (EMA) also recommended approval for the same patient population. The current recommended initial dose is 300 mg intravenous (IV) infusion followed 2 weeks later by a second 300 mg IV infusion. The recommended maintenance dose is a single 300 mg IV infusion every 6 months thereafter, starting 6 months from the first infusion (7).

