NMOSD disease burden and clinical characteristics up to the index date will include the presence of each of the diagnoses part of the NMOSD core symptom, disease duration, AQP4 and MOG seropositivity, NMOSD-associated conditions, history of relapses, and previous acute and maintenance therapies.

Disease duration will be estimated as the difference between the index date and the first NMOSD diagnosis date.

Where available, laboratory results most recent to the index date will be used to classify patients according to the presence of autoantibodies against AQP4 and MOG. Patients will be classified as positive, negative or unknown serology. As it is recommended to repeat AQP4-antibody testing if the result is non-conclusive or negative, the presence of at least one positive result will be sufficient to classify the patient as positive. Thus, data on serology during follow-up will be also analysed to present the most updated serology status of the patients.

Information on spinal cord and brain Magnetic Resonance Imaging (MRI) scans performed in the previous year will be extracted whenever available in the data sources. Patients will be defined as having had performed spinal MRI only, brain MRI only, spinal and brain MRI or no MRI scan in the previous year.

NMOSD as an autoimmune disease has been reported to coincide with other disorders including systemic autoimmune diseases, organ-specific autoimmune diseases, and other diseases with possible immunologic pathogenesis (13). The association of clinical or even subclinical autoimmunity is a supportive feature for the diagnosis of the disease (14).

NMOSD-associated conditions listed below will be identified by the respective ICD-9/ICD-10 codes (**Error! Reference source not found.** in Annex 3):

- Hypothyroidism
- Pernicious anemia
- Ulcerative colitis
- Myasthenia gravis
- Idiopathic thrombocytopenic purpura
- Hemiplegia/paraplegia
- Bladder dysfunction
- Neuropathic pain
- Antiphospholipid syndrome
- Sarcoidosis
- Scleroderma
- Sjogren’s syndrome
- Systemic lupus erythematosus
- Dorsalgia
- Disorders of lipoprotein metabolism and other lipidemias
- Other acute disseminated demyelination
- Disorders of refraction and accommodation
- Visual disturbances
- Disturbances of skin sensation
- Somatoform disorders
- Other dorsopathies, not elsewhere classified

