Infections	Available upon request	Available upon request

Abbreviations: ICD-9/ICD-10, 9th/10th Revision of International Classification of Diseases; CM, Clinical Modification
*ICD-X-CM codes will be translated into local ICD-X codes and provided in SAP

Table 7 NMOSD-Associated Conditions

NMOSD-associated Conditions	Diagnosis ICD-9-CM Codes*	Diagnosis ICD-10-CM Codes*
Hypothyroidism	244.x	E89.0, E03.2, E03.8, E03.9
Pernicious anemia	281.0, 281.1	D51.x
Ulcerative colitis	556.x [excl. 556.2 and 556.3]	K51.xx [excl. K51.2x and K51.3x]
Myasthenia gravis	358.0x	G70.0x
Idiopathic thrombocytopenic purpura	446.6	M31.1
Hemiplegia/paraplegia	334.1, 342.x, 343.x, 344.0x-344.6x, 344.9	G11.4, G81.xx, G80.x, G83.0, G83.1x, G83.2x, G83.3x, G83.4, G83.9, G82.xx
Bladder dysfunction	788.30, 788.31, 788.33, 788.34, 788.36, 788.37, 788.39-788.43, 596.xx	N30.xx, N31.x, N32.xx, N33
Neuropathic pain	353.x, 354.x, 355.x, 356.x, 357.x, 250.6, 729.2, 782	E08.40-E08.42, E09.40, E09.42, E10.40-E10.42, E11.40-E11.42, E13.40-E13.42, G50.0, G50.1, G54.x, G55.x, G56.x, G57.x, G58.x, G60.x, G61.x, G62.x, G63, G64, G65.x, G90.5x, M05.5x, M79.2, M54.1, R20
Antiphospholipid syndrome	289.81	D68.61
Sarcoidosis	135	D86.xx
Scleroderma	357.4, 359.6, 517.2, 701.0, 710.1	M34.xx, L90.0, L94.0, L94.1, L94.3
Sjogren's syndrome	710.2	M35.0x
Systemic lupus erythematosus	710	M32.xx
Dorsalgia	724.5	M54
Disorders of lipoprotein metabolism and other lipidemias	272.0, 272.1, 272.2, 272.3, 272.4, 272.5, 272.9	E78
Other acute disseminated demyelination	341.9	G36.9
Disorders of refraction and accommodation	367	H52
Visual disturbances	368	H53
Disturbances of skin sensation	782	R20
Somatoform disorders	300.81	F45
Other dorsopathies, not elsewhere classified	723.2, 723.3, 723.8, 723.9	M53

NMOSD-associated Conditions	Diagnosis ICD-9-CM Codes*	Diagnosis ICD-10-CM Codes*
-----------------------------	------------------------------	-------------------------------

Abbreviations: ICD-9/ICD-10, 9th/10th Revision of International Classification of Diseases; CM, Clinical Modification; NMOSD, Neuromyelitis optica spectrum disorder

*ICD-X-CM codes will be translated into local ICD-X codes and provided in SAP

Table 8 Acute Treatments

Name of Agent	Description	Coding
Intravenous Corticosteroids*	H02 - Corticosteroids for systemic use	ATC
Intravenous Immunoglobulin (IVIG)*	J06B - Immunoglobulins	ATC
	8-810.w Human immunoglobulin, polyvalent	OPS
Plasma Exchange (PLEX)	6A550Z3 - Pheresis of Plasma, Single	ICD-10-PCS

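### Table 7 identifies idiopathic thrombocytopenic purpura by the ICD codes of a different disease, thrombotic microangiopathy

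*Protocol*

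**What the plan says.** Section 6.3.2 of the protocol lists 21 NMOSD-associated conditions, "Idiopathic thrombocytopenic purpura" among them, and states that "NMOSD-associated conditions listed below will be identified by the respective ICD-9/ICD-10 codes". The codes are in Annex 3, Table 7, where the row reads "Idiopathic thrombocytopenic purpura 446.6 M31.1". The same table, with the same row, also appears within the text of section 6.3.2. A footnote to the table says that the SAP will give the local equivalents of the listed codes. Section 6.3 adopts ICD-9 and ICD-10, or local modifications, as the means of defining these conditions. Objective 1 in section 5 covers NMOSD-related clinical characteristics at first treatment, and section 6.3.2 counts the associated conditions among them.

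**The concern.** The label names one disease and the codes name another. Because the codes are the operational definition, the data extraction will follow them and ignore the label. The report would then print a count for idiopathic thrombocytopenic purpura that consists of patients with thrombotic microangiopathy, and patients with the named condition would be shown as free of it.

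The mistake is hard to catch downstream. The ICD-9 and ICD-10 columns agree with each other, so a concordance check between them would pass. Section 6.3.2 treats coexisting autoimmunity as supportive of the NMOSD diagnosis, so the row is there for a reason and a wrong count misinforms about it.

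**Working it through.** No sample size, rate or interval is involved, and the plan states no figure to reproduce. The check is a reading of the code lists.

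1. **What the row contains.** Table 7 gives 446.6 and M31.1 and nothing else. The repeat in section 6.3.2 is identical.

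2. **What the codes mean.** In the ICD, 446.6 and M31.1 are thrombotic microangiopathy (thrombotic thrombocytopenic purpura). Idiopathic or immune thrombocytopenic purpura is 287.31 in ICD-9-CM and D69.3 in ICD-10-CM. The protocol adopts the ICD but does not reproduce its rubrics, so this step rests on the classification itself.

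3. **Whether the protocol's own coding fits.**
   - Table 6 puts neighbouring codes of the same two categories under rheumatic disease: 446.5 in the ICD-9 column, and in the ICD-10 column "M31.5, M31.6, M32.xx, M34.xx, M35.0x, M33.xx, M05.xxx, M35.3".
   - Table 7 codes its haematological conditions in the 28x and D ranges: "Pernicious anemia 281.0, 281.1 D51.x", and antiphospholipid syndrome as 289.81 / D68.61.
   - The thrombocytopenic purpura row departs from that pattern in both columns. This agrees with step 2 but does not by itself prove what 446.6 and M31.1 denote.

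4. **Whether the right codes appear elsewhere.** Tables 2, 6, 7 and 12 list no code from category 287 or D69. No other listed variable would pick these patients up.

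5. **What the row would report.** Let *a* be the number of initiators coded 287.31 or D69.3, *b* the number coded 446.6 or M31.1, and *c* the number with codes from both groups. The row reports *b*, whereas the label promises *a*. Of the *a* patients with the named condition, only *c* are counted and *a* − *c* are missed. Of the *b* patients counted, *b* − *c* have no code for the named condition. The documents give no value for *a*, *b* or *c*, so no patient number follows.

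6. **Whether later steps repair it.** Translating 446.6 / M31.1 faithfully into local codes carries the same disease into every source. Section 6.3.2 allows the variable list to be refined for what a database holds and how specific it is, which is not a route for correcting a wrong code.

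**The case against.** Four things can be said for leaving it.

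- **The code meanings are not in the document.** True, and the neighbouring codes in Table 6 are only supportive. But the protocol makes the ICD its definition, so reading a code by its ICD meaning is reading the plan as it will be executed.
- **The repeat in section 6.3.2 is not independent confirmation.** This stands. The table sits in the middle of a sentence on acute treatments, near a broken cross-reference, and was most likely pulled in from the annex. It shows only that there are two places to correct.
- **The effect is small.** This also stands. It is one descriptive row. A rare condition split over several sources may fall under the small-number masking of section 6.7.1. Section 6.9 already warns that associated conditions may be misclassified, although it attributes this to diagnosis and coding practice and not to the study's own code list.
- **The SAP could still put it right.** It could, but the protocol commits the SAP only to translation, and an analyst has no reason to question two columns that agree.

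A reader might also infer that Table 7 misses severe visual disability, because section 4.1 describes "unilateral or bilateral loss of visual acuity that can lead to blindness" while no table lists 369 / H54 (blindness and low vision). The documents do not support calling that an error. The row "Visual disturbances 368 H53" carries codes that fit its label, and no row undertakes to record blindness. Optic neuritis is captured through Table 2 and described at baseline under section 6.3.2, so a patient blinded by it need not appear free of visual involvement. Nor is there a basis for saying that initiators would look less disabled than they are: the protocol builds no disability measure from these rows and gives no figures from which to count such patients.

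**Conclusion.** The row is wrong as written. Following the protocol would report thrombotic microangiopathy under the name of idiopathic thrombocytopenic purpura and would miss every patient coded only with the latter. The conclusion assumes the standard ICD meanings of the four codes and a faithful translation into local codes.

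The consequence is confined to one of 21 descriptive baseline conditions under Objective 1, including its subgroup tables. Eligibility, exposure, treatment patterns, the incidence of adverse events of special interest and the study size do not depend on it. It is a minor correction, worth making because it is certain and nearly free.

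**What to change.** In Annex 3, Table 7, replace 446.6 / M31.1 with 287.31 / D69.3 in the idiopathic thrombocytopenic purpura row. Make the same change in the repeat in section 6.3.2, or replace that repeat with a working reference to the annex. Do this before the local code lists are drawn up, so that each data source starts from the right codes. The cost is one row of a code list, with no new data and negligible programming.

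Optionally, the authors may add a row for blindness and low vision (369 / H54) or state that it is out of scope. That would be an addition to the variable list and not a correction.
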